5 STUDY ACTIVITIES

5.1 Eligibility Criteria

Subjects must meet all the following criteria in order to be included in the study. Anything other than a positive response to the questions below will result in exclusion from study participation.

Consent and Demographics

- 1. Subjects should have successfully completed treatment in Study M16-046, without developing any permanent discontinuation criteria.
- 2. Subject must voluntarily sign and date an informed consent, approved by an Independent Ethics Committee (IEC)/Institutional Review Board (IRB), prior to the initiation of any studyspecific procedures and comply with the requirements of this study protocol.

- 3. Subject remains eligible to continue treatment in the long-term extension study by not meeting any of the criteria during Study M16-046 that would have warranted study drug discontinuation:
 - a) Rescue treatment was administered outside of the protocol-specified parameters in Study M16-046;
 - b) Initiation of any systemic rescue therapy for AD as defined in Study M16-046;
 - c) Any subject with an EASI score worsening of 25% or more compared with their Study M16-046 Baseline EASI score at any 2 consecutive scheduled study visits (after a trial of rescue treatment, if appropriate);
 - d) Anaphylactic reaction or other severe systemic or local reaction to study drug injection;
 - e) Clinically significant abnormal laboratory results or AEs, which rule out continuation of the study drug;
 - f) The investigator believes it is in the best interest of the subject;
 - g) The subject requests withdrawal from the study;
 - h) Eligibility criteria violation was noted after the subject started study drug, when continuation of the study drug would place the subject at risk;
 - i) Introduction of prohibited medications or dosages when continuation of the study drug would place the subject at risk;
 - j) Subject is non-compliant with TB prophylaxis (if applicable) or develops active TB at any time during the study;
 - k) The subject becomes pregnant or plans to become pregnant while on study drug;
 - I) Malignancy, except for localized non-melanoma skin cancer (NMSC) or carcinoma in-situ of the cervix;
 - m) Subject develops a GI perforation;
 - n) Subject is significantly non-compliant with study procedures which would put the subject at risk for continued participation in the trial in consultation with the AbbVie TA MD or TA SD:
 - o) An ECG change considered clinically significant and with reasonable possibility of relationship to study drug, OR a confirmed absolute Fridericia's correction formula (QTcF) value > 500 msec in adults OR a change of QT interval corrected (QTc) interval > 60 msec from baseline.

Contraception

- 4. Females of childbearing potential must not have a positive urine pregnancy test at the Baseline Visit prior to study drug dosing.
- 5. If female, subject must be postmenopausal OR permanently surgically sterile OR for females of childbearing potential practicing at least one protocol-specified method of birth control (refer to Section 5.2), that is effective from the Baseline Visit through at least 30 days after the last dose of study drug.

- 6. Female subject must not be pregnant, breastfeeding, or considering becoming pregnant during the study or for approximately 30 days after the last dose of the study drug.
- 7. Additional local requirements may apply (see Section 5.2).

Prior and Concomitant Therapy

8. Subjects should not be taking excluded concomitant medication at the end of treatment in Study M16-046, according to the M16-046 protocol.

Medical History

9. Any ongoing adverse event from Study M16-046 or medical condition prior to continuing in the long-term extension study which would put the subject at risk by participating in the open label treatment extension study.

5.2 Contraception Recommendations

Contraception Recommendations for Females

Subjects must follow the following contraceptive guidelines as specified:

- Females, Non-Childbearing Potential
- Females do not need to use birth control during or following study drug treatment if considered of non-childbearing potential due to meeting any of the following criteria:
 - Postmenopausal, age > 55 years with no menses for 12 or more months without an alternative medical cause.
 - Postmenopausal, age ≤ 55 years with no menses for 12 or more months without an alternative medical cause AND a follicle-stimulating hormone (FSH) level > 40 IU/L.
 - Permanently surgically sterile (bilateral oophorectomy, bilateral salpingectomy, or hysterectomy)
 - Females who have not experienced menarche (at least one menstrual period)
- Females of Childbearing Potential
- Females of childbearing potential must avoid pregnancy while taking study drug and for at least 30 days after the last dose of study drug. Females must commit to one of the following methods of highly effective birth control:
 - Combined (estrogen- and progestogen-containing) hormonal birth control (oral, intravaginal, transdermal, injectable) associated with inhibition of ovulation.
 - Progestogen-only hormonal birth control (oral, injectable, implantable) associated with inhibition of ovulation.
 - Bilateral tubal occlusion/ligation (can be via hysteroscopy, provided a hysterosalpingogram confirms success of the procedure).

- Intrauterine device (IUD).
- Intrauterine hormone-releasing system (IUS).
- Vasectomized sexual partner (the partner has received medical confirmation of the surgical success of the vasectomy and is the sole sexual partner of the trial subject).
- Practice true abstinence (unless not acceptable per local practices), defined as: refraining
 from heterosexual intercourse when this is in line with the preferred and usual lifestyle of
 the subject (periodic abstinence [e.g., calendar, ovulation, symptothermal, post-ovulation
 methods] and withdrawal are not acceptable).

If required per local practices, females of childbearing potential must commit to using 2 methods of contraception (either 2 highly effective methods or 1 highly effective method combined with 1 effective method). Effective methods of birth control are the following:

- Progestogen-only oral hormonal contraception, where inhibition of ovulation is not the primary mode of action, initiated at least 30 days prior to Baseline.
- Male or female condom with or without spermicide.
- Cap, diaphragm, or sponge with spermicide.
- A combination of male condom with a cap, diaphragm, or sponge with spermicide (double barrier method).

Contraception recommendations related to use of concomitant therapies prescribed per standard of care should be based on the local label.

At each visit, the study staff should review the pregnancy avoidance recommendations with each female of childbearing potential and document this discussion in the subject's source records.

5.3 Prohibited Medications and Therapy

JAK Inhibitors

Concomitant oral and topical exposure to any other JAK inhibitors (including but not limited to ruxolitinib [Jakafi®], tofacitinib [Xeljanz®], baricitinib, abrocitinib [PF-04965842], and filgotinib) is not allowed.

Targeted Biologic Therapies

Current and concomitant biologic therapies and biosimilar versions of biologic drugs are prohibited during treatment with the study drug. Examples of biologic therapies include but are not limited to the following:

- abatacept
- adalimumab
- anakinra
- belimumab

- certolizumab
- dupilumab
- efalizumab
- etanercept
- golimumab
- guselkumab
- infliximab
- ixekizumab
- natalizumab
- omalizumab
- risankizumab
- rituximab
- secukinumab
- tocilizumab
- ustekinumab
- vedolizumab

Other Non-Biologic Systemic Therapy

Concomitant treatment with systemic non-steroidal systemic immunosuppressive drugs is prohibited during treatment with study drug, including but not limited to:

- methotrexate
- cyclosporine
- azathioprine
- PDE4-Inhibitors (e.g., apremilast)
- mycophenolate mofetil

See also Section 5.4 Rescue Therapy for further details on allowed rescue.

Corticosteroids

Concomitant treatment with systemic corticosteroids (oral, intravenous, intramuscular) and intralesional corticosteroids for the treatment of AD is prohibited during treatment with study drug.

Inhaled, ophthalmic drops, and nasal corticosteroid formulations are allowed throughout the study.

See also Section 5.4 Rescue Therapy for further details on allowed rescue.

Investigational Drugs

Investigational drugs are prohibited during treatment with study drug.

Phototherapy, Tanning Booth, and Extended Sun Exposure

Ultra-violet (UV) B or UVA phototherapy including psoralen and ultraviolet A (PUVA) or laser therapy are not allowed during the study. Tanning booth use or extended sun exposure that could affect disease severity or interfere with disease assessments are not allowed during treatment with study drug.

Topical Therapy

No topical treatments for AD should be started for the duration of the treatment with study drug except for rescue treatment (see Section 5.4 Rescue Therapy). This includes but is not limited to calcineurin inhibitors, corticosteroids, prescription moisturizers or moisturizers containing additives such as ceramide, hyaluronic acid, urea, or filaggrin. Topical emollient treatments are allowed.

Topical anti-infectives, topical antihistamines, and bleach baths are allowed per investigator discretion for the remainder of the study.

If there is any question regarding whether a concomitant medication may be used during the study, the study site should contact the AbbVie Therapeutic Area Medical Director (TA MD).

Vaccines

Live vaccinations are prohibited during study participation including at least 30 days (or longer if required locally) after the last dose of study drug.

Examples of live vaccines include, but are not limited to, the following:

- Monovalent live influenza A (H1N1) (intranasal);
- Seasonal trivalent live influenza (intranasal);
- Zostavax (herpes zoster, live attenuated);
- Rotavirus;
- Varicella (chicken pox);
- Measles-mumps-rubella or measles-mumps-rubella-varicella;
- Oral polio vaccine;
- Smallpox;
- Yellow fever;
- Bacille Calmette-Guérin (Bacilli Calmette-Guérin);
- Typhoid (oral).

Administration of inactivated (non-live) vaccines is permitted prior to or during the study according to local practice guidelines. Examples of common vaccines that are inactivated, toxoid or biosynthetic include, but are not limited to, injectable influenza vaccine, pneumococcal, Shingrix (zoster vaccine, recombinant, adjuvanted), and pertussis (Tdap) vaccines.

Cannabis

Use of medicinal and recreational marijuana is prohibited during the study.

Traditional Chinese Medicine

Traditional oral or parenteral Chinese medicine is not permitted during the study as these may interfere with upadacitinib metabolism and exposure and may impact efficacy and safety of upadacitinib treatment.

Strong CYP3A Inhibitors or Inducers

Systemic use of known strong cytochrome P450 3A isoform subfamily (CYP3A) inhibitors or strong CYP3A inducers is not allowed through the end of the study. The most common strong CYP3A inhibitors and inducers are listed in Table 1.

Table 1. Examples of Commonly Used Strong CYP3A Inhibitors and Inducers

Strong CYP3A Inhibitors	Strong CYP3A Inducers
Boceprevir	Avasimibe
Clarithromycin	Carbamazepine
Cobicistat	Phenytoin
Conivaptan	Rifampin (Rifampicin)
Grapefruit (fruit or juice)	Rifapentine
Indinavir	St. John's Wort
Itraconazole	
Ketoconazole	
Lopinavir/Ritonavir	
Mibefradil	
Nefazodone	
Nelfinavir	
Posaconazole	
Ritonavir	
Saquinavir	
Telaprevir	
Telithromycin	
Troleandomycin	
Voriconazole	

Elective and Emergency Surgeries

Elective surgery will not be allowed during the study.

If the subject must undergo emergency surgery, the study drug should be interrupted at the time of the surgery. See Section 5.8 Study Drug Administration for allowed study drug interruption parameters.

5.4 Prior and Concomitant Therapy

Any medication or vaccine (including over-the-counter or prescription medicines, vitamins and/or herbal supplements) that the subject is receiving at the time of the Baseline visit and/or receives during the study, must be recorded along with the reason for use, date(s) of administration including start and end dates, and dosage information including dose, route and frequency on the appropriate electronic case report form (eCRF). Also, medications taken for AD since date of diagnosis (based on subject recollection and available medical records) should be reviewed.

If there are any questions regarding concomitant or prior therapies, the AbbVie TA MD should be contacted.

Required Concomitant Medications

Twice daily use of an additive-free, bland emollient that was used during Study M16-046 should be continued for the duration of Study M19-850.

Note: Subject may use prescription moisturizers or moisturizers containing ceramide, urea, filaggrin degradation products or hyaluronic acid if such moisturizers were initiated before Study M16-046 Baseline visit.

Rescue Therapy

Rescue treatment for AD may be provided, if medically necessary, at the discretion of the investigator.

Investigators should attempt to limit the first step of rescue therapy to topical medications and escalate to systemic medications only for those subjects who do not respond adequately after at least 7 days of topical treatment.

If a subject needs rescue treatment with a systemic agent (including but not limited to corticosteroids, cyclosporine, methotrexate, mycophenolate mofetil, azathioprine) or phototherapy, study drug should be permanently discontinued prior to the initiation of rescue systemic agent or phototherapy and subject should be discontinued from the study.

Investigators should conduct efficacy and safety assessments (e.g., disease severity scores, safety labs) before administering any rescue treatment. An unscheduled visit may be used for this purpose if necessary.

5.5 Withdrawal of Subjects and Discontinuation of Study

Subjects may withdraw from the study completely (withdrawal of informed consent) for any reason at any time.

Subjects can request to be discontinued from participating in the study at any time for any reason including, but not limited to, disease progression or lack of response to treatment. The investigator may discontinue any subject's participation at any time for any reason, including but not limited to, lack of

response to treatment, an AE, safety concerns, or failure to comply with the protocol. Refer to Section 6.2 for additional discontinuation criteria relating to Toxicity Management of serious infections, gastrointestinal perforation, cardiovascular and thromboembolic events, malignancy, electrocardiogram (ECG) abnormality, and select laboratory abnormalities.

Subjects will have study drug discontinued immediately if any of the following occur:

- Rescue treatment is administered outside of the parameters described in Section 5.4 (Rescue Therapy).
- Initiation of any systemic rescue therapy for AD.
- Permanent discontinuation from study drug will be mandatory after Study M19-850 baseline for any subject with an EASI score worsening of 25% or more compared with their Study M16-046 Baseline EASI score at any 2 consecutive scheduled study visits in this study (after a trial of rescue treatment, if appropriate; see Section 5.4 Rescue Therapy). For example, permanent study drug discontinuation would apply at Week 4 if EASI score worsening criteria are met at Study M19-850 Baseline and Week 4 without rescue therapy given at Study M19-850 Baseline. Permanent study drug discontinuation would apply at Week 8 if EASI score worsening criteria are met at Week 4 and Week 8 with rescue therapy given at Study M19-850 Baseline. This rule applies similarly to later timepoints.
- Clinically significant abnormal laboratory results or AEs, which rule out continuation of the study drug, as determined by the investigator and the AbbVie Therapeutic Area Medical/Scientific Director.
- The investigator believes it is in the best interest of the subject.
- The subject requests withdrawal from the study.
- Eligibility criteria violation was noted after the enrollment of the subject in the study, when continuation of the study drug would place the subject at risk as determined by the AbbVie Therapeutic Area Medical/Scientific Director.
- Introduction of prohibited medications or dosages when continuation of the study drug would place the subject at risk, as determined by the AbbVie Therapeutic Area Medical/Scientific Director.
- Subject is non-compliant with tuberculosis (TB) prophylaxis (if applicable) or develops active TB at any time during the study.
- The subject becomes pregnant or plans to become pregnant while on study drug.
- Malignancy, except for localized non-melanoma skin cancer (NMSC) or carcinoma in-situ of the cervix.
- Subject is significantly non-compliant with study procedures which would put the subject at risk
 for continued participation in the trial in consultation with the AbbVie Therapeutic Area
 Medical/Scientific Director.
- Subject develops a GI perforation (defined as acute, spontaneous perforation of the gastrointestinal tract that requires inpatient medical care or urgent surgical intervention other than appendicitis or mechanical injury). See also Section 6.2 Toxicity Management.

- An ECG change considered clinically significant and with reasonable possibility of relationship to study drug, OR a confirmed absolute Fridericia's correction formula (QTcF) value > 500 msec in adults OR a change of QT interval corrected (QTc) interval > 60 msec from baseline.
- Confirmed diagnosis of deep vein thrombosis, pulmonary embolus, or non-cardiac, non-neurologic arterial thrombosis.

The study will be discontinued or terminated in case of an unacceptable risk, any relevant toxicity, or a negative change in the risk:benefit assessment. This might include the occurrence of AEs with a character, severity, or frequency that is new in comparison to the existing risk profile. In addition, any data deriving from other clinical trials or toxicological studies that negatively influence the risk:benefit assessment may cause discontinuation or termination of the study.

AbbVie may terminate this study prematurely, either in its entirety or at any site. The investigator may also stop the study at his/her site if he/she has safety concerns. If AbbVie terminates the study for safety reasons, AbbVie will promptly notify the investigator.

For subjects to be considered lost to follow-up, reasonable attempts must be made to obtain information on the final status of the subject. At a minimum, 2 telephone calls must be made and one certified letter must be sent and documented in the subject's source documentation.

COVID-19 Pandemic-Related Acceptable Protocol Modification

During the COVID 19 pandemic, it has been necessary to employ mitigation strategies to enable the investigator to ensure subject safety and continuity of care. Acceptable mitigation strategies are identified and included in the Operations Manual in Appendix F.

The investigator should contact the sponsor medical contact before discontinuing a subject from the study for a reason other than "planned per protocol," to ensure that all acceptable mitigation steps have been explored.

Refer to the Operations Manual in Appendix F for details on how to handle study activities/procedures.

Interruption/Discontinuation of Study Drug Due to COVID-19 Infection

Delays in study drug dosing due to the COVID-19 pandemic must be discussed with the AbbVie medical contact, along with the possibility of premature discontinuation from the study drug dosing period. Follow subsequent protocol Section 5.6 for subjects who discontinue study drug.

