6.2 Toxicity Management

The toxicity management of AEs, including AESI consists of safety monitoring (review of AEs on an ongoing basis, and periodical/ad hoc review of safety issues, interruption of study drug dosing with

appropriate clinical management if applicable, and discontinuation of the subjects from the study drug). The management of specific AEs and laboratory parameters is described below.

Management of Serious Infections

Subjects should be closely monitored for the development of signs and symptoms of infection during and after treatment with study drug. Study drug should be interrupted if a subject develops a serious infection. A subject who develops a new infection during treatment with study drug should undergo prompt diagnostic testing appropriate for an immunocompromised subject. As appropriate, antimicrobial therapy should be initiated, and the subject should be closely monitored. Study drug may be restarted once the infection has been successfully treated. Subjects who develop active TB must be permanently discontinued from study drug. If a subject develops zoster, or shows infection with or reactivation of any other herpes virus (e.g., HSV, VZV, EBV, CMV), any study drug should at least be temporarily interrupted until the episode resolves, or discontinued as patient safety requires.

Management of Herpes Zoster

If a subject develops herpes zoster, consider temporarily interrupting study drug until the episode resolves. Serious AEs of herpes zoster should be reported as serious infections.

Management of Serious Gastrointestinal Events

Subjects presenting with the onset of signs or symptoms of a gastrointestinal perforation should be evaluated promptly for early diagnosis and treatment. Subjects with acute, spontaneous perforation of the gastrointestinal tract that requires inpatient medical care or urgent surgical intervention (except for appendicitis or mechanical injury) must be permanently discontinued from study drug.

Management of Thrombosis Events

Subjects who develop symptoms of thrombosis should be promptly evaluated and treated appropriately. If the diagnosis of deep vein thrombosis, pulmonary embolus or non-cardiac, non-neurologic arterial thrombosis is confirmed, the subject must be discontinued from study drug.

Management of Malignancy

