Subjects who develop malignancy other than NMSC or carcinoma in-situ of the cervix must be discontinued from the study drug. Information including histopathological results should be queried for the confirmation of the diagnosis. Periodic skin examination is recommended for subjects who are at increased risk of skin cancer.

Management of ECG Abnormality

Subjects must be discontinued from study drug for an ECG change considered clinically significant and with reasonable possibility of relationship to study drug, OR a confirmed absolute Fridericia's correction formula (QTcF) value > 500 msec, OR a change of QTc interval > 60 msec from Baseline.

COVID-19

Interrupt study drug in subjects with a confirmed diagnosis of COVID-19. Consider interrupting study drug in subjects with signs and/or symptoms and suspicion of COVID-19. The COVID-19 eCRF must be completed.

Management of Select Laboratory Abnormalities

For any given laboratory abnormality, the investigator should assess the subject, apply the standard of care for medical evaluation and treatment following any local guidelines. Specific toxicity management guidelines for abnormal laboratory values are described in Table 5, and may require a supplemental eCRF to be completed (see Protocol Section 6.1 [Complaints and AEs]). All abnormal laboratory tests that are considered clinically significant by the investigator will be followed to a satisfactory resolution. If a repeat test is required per Table 5, the repeat testing must occur as soon as possible.

 Table 5.
 Specific Toxicity Management Guidelines for Abnormal Laboratory Values

Laboratory Parameter	Toxicity Management Guideline
Hemoglobin	If hemoglobin < 8 g/dL interrupt study drug dosing and confirm by repeat testing with a new sample
	• If hemoglobin decreases ≥ 3.0 g/dL from Baseline, without an alternative etiology, interrupt study drug dosing and confirm by repeat testing with new sample.
	• If hemoglobin decreases ≥ 3.0 g/dL from Baseline and an alternative etiology is known or the hemoglobin value remains in the normal reference range, the subject may remain on study drug at the investigator's discretion.
	If confirmed, continue to withhold study drug until hemoglobin value returns to normal reference range or its Baseline value.
Absolute neutrophil count (ANC)	 If confirmed < 1000/μL by repeat testing with new sample, interrupt study drug dosing until ANC value returns to normal reference range or its Baseline value.

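### Protocol 5.5 and 6.2 word the mandatory malignancy stop differently for non-localized NMSC, 5.5 points to cardiovascular criteria that 6.2 lacks, and two hemoglobin bullets in Table 5 overlap

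*Protocol*

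**What the plan says.** **Malignancy.** Protocol 5.5 lists events that require study drug to be stopped immediately, any one of which is enough. One is "Malignancy, except for localized non-melanoma skin cancer (NMSC) or carcinoma in-situ of the cervix". Protocol 6.2, under the management of malignancy, says: "Subjects who develop malignancy other than NMSC or carcinoma in-situ of the cervix must be discontinued from the study drug". The qualifier *localized* appears in the first and not in the second.

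**Cardiovascular events.** Before that list, Protocol 5.5 gives a cross-reference: "Refer to Section 6.2 for additional discontinuation criteria relating to Toxicity Management of serious infections, gastrointestinal perforation, cardiovascular and thromboembolic events, malignancy", followed by ECG abnormality and select laboratory abnormalities. In 6.2 the rule for vascular events is that if "deep vein thrombosis, pulmonary embolus or non-cardiac, non-neurologic arterial thrombosis is confirmed, the subject must be discontinued from study drug". The ECG rule begins: "Subjects must be discontinued from study drug for an ECG change considered clinically significant and with reasonable possibility of relationship to study drug". Both rules are also in the 5.5 list.

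**Hemoglobin.** In Protocol Table 5, the second hemoglobin bullet calls for interruption and a repeat test when hemoglobin falls by 3.0 g/dL or more from Baseline without an alternative etiology. The third bullet covers a fall of the same size with a known cause. Its alternative condition, with the instruction that follows both, reads: "the hemoglobin value remains in the normal reference range, the subject may remain on study drug at the investigator's discretion".

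**The concern.** Sections 5.5 and 6.2 both instruct sites on when to stop study drug, and a site handling an event may well open only the toxicity section. If the two texts differ, the same event can be handled differently across up to 150 sites.

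AEs leading to discontinuation of study drug are among the primary safety endpoints (Protocol 3.2, SAP 3.1). Under Protocol 5.6, stopping study drug early ends participation altogether, and AE collection closes 30 days after the last dose (Protocol 6.1). A difference in stopping therefore also changes what is observed afterwards. SAP Appendix A counts subjects who met a withdrawal criterion and were not withdrawn, and that count needs one agreed set of criteria.

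The pointer raises a related worry. Adjudicated cardiovascular events are an AESI, and myocardial infarction, heart failure and stroke have their own supplemental forms (Protocol 6.1, Table 4). A site with such an event is directed to a criterion that it will not find.

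**Working it through.** The point rests on no sample size, rate or formula, so the check is a comparison of texts. The table shows what each section requires when read alone.

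| Event | Protocol 5.5 | Protocol 6.2 | Do they agree? |
|---|---|---|---|
| Localized NMSC | Exempt | Exempt | Yes |
| Carcinoma in situ of the cervix | Exempt | Exempt | Yes |
| Non-localized NMSC | Mandatory stop | No mandatory stop | **No** |
| Other malignancy | Mandatory stop | Mandatory stop | Yes |
| Confirmed DVT, PE, or arterial thrombosis outside heart and nervous system | Mandatory stop | Mandatory stop | Yes |
| Specified ECG or QTc change | Mandatory stop | Mandatory stop | Yes |
| Defined GI perforation | Mandatory stop | Mandatory stop | Yes |
| Active TB | Mandatory stop | Mandatory stop | Yes |
| Myocardial infarction, stroke | No specific criterion; refers to 6.2 | No criterion | Yes, but the reference leads nowhere |

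**Step 1, malignancy.** Of the event-based stop rules compared here, malignancy is the only one whose substance changes between the sections, and only for non-localized NMSC.

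**Step 2, the pointer.** The headings in 6.2 are serious infections, herpes zoster, serious gastrointestinal events, thrombosis, malignancy, ECG abnormality, COVID-19 and laboratory abnormalities. Each topic named in the 5.5 reference has a counterpart except cardiovascular events. The thrombosis rule cannot fill the gap, because its arterial part is restricted to events that are neither cardiac nor neurologic. The ECG rule cannot either, because 5.5 names ECG as a separate topic. Protocol 6.3 describes adjudication and sets no stopping criterion. Section 6.2 is unbroken in the text available, so the absence is not a redaction.

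**Step 3, hemoglobin.** Take a fall of 3.0 g/dL or more.

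- Etiology known: only the third bullet applies.
- Etiology not known, value below the normal range: only the second of these two bullets applies.
- Etiology not known, value in the normal range: both apply. One says interrupt; the other allows the subject to remain on drug. No precedence is stated.

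**Step 4, what could change in the analysis.** For a non-localized NMSC, one reading gives a discontinuation due to an AE and the other does not. Patient-years in SAP 10.2.4 are built on the first-to-last-dose duration in SAP 6.0, so exposure after the event differs too. If the subject continues, the Appendix A category applies under 5.5 but would be missed by someone checking against 6.2 alone. For hemoglobin the matter is interruption. A subject who restarts keeps the same first and last dose dates, so the SAP 6.0 duration need not change.

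**The case against.** The strongest reply is that the two sections can be read together without contradiction. Section 5.5 acts on any listed event and calls the criteria in 6.2 additional. Section 6.2 leaves NMSC out of its own mandatory stop but nowhere says that such a subject must continue. A site that applies both sections would stop for a non-localized NMSC. This stands, and it limits the problem to sites that work from 6.2 alone.

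Several stronger readings are tempting, and the documents do not support them.

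- *That stopping after a myocardial infarction or stroke depends on the section read.* It does not. Neither section has a mandatory criterion, and both events fall under the general bullets of 5.5 on AEs that rule out continuation and on the investigator's view of the subject's best interest. The fault is an over-broad pointer.
- *That the Appendix A deviation count has no definition.* Section 5.5 does list the criterion. The risk is uneven application.
- *That the AESI counts are affected.* SAP Appendix B identifies malignancy and anemia by MedDRA queries and MACE from adjudication output. The event counts whether or not the subject then stops.
- *That the number of subjects follows from about 600 subjects and an assumed event rate.* A rate for malignancy, NMSC or cardiovascular events as a whole does not size non-localized NMSC, the only group whose mandatory stop differs between the sections. The higher NMSC rate on 30 mg than on 15 mg in the RA studies (Protocol 2.2) does not size it either.
- *That the hemoglobin overlap is a permanent-stop conflict.* It concerns interruption, for which Protocol 5.8 sets no time limit. The third bullet can be read as an exception to the second. That reading is possible, but Table 5 does not state it.

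**Conclusion.** The point holds as a fault of internal consistency with three parts: one differing mandatory-stop rule (non-localized NMSC), one reference to cardiovascular criteria that are not there, and one pair of overlapping hemoglobin instructions. They are safety instructions, so they should be corrected even though the impact is small.

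The size cannot be calculated. The documents give no rate for non-localized NMSC and none for hemoglobin falls of this kind within the normal range; the number of affected subjects is probably very small. The possible effects are on how individual subjects are handled, on the count of AEs leading to discontinuation, on exposure after the event and, for non-localized NMSC, on consistent use of the deviation category.

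The conclusion assumes that the protocol text available is complete for 5.5 and 6.2. The Operations Manual was not available, but 5.5 sends sites to 6.2 for these criteria, so the pointer is faulty whatever the manual contains. No view is taken on which clinical rule is right.

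**What to change.** Reconcile the texts, with the sponsor's medical team deciding the content:

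1. Use the same malignancy exemption in Protocol 5.5 and 6.2.
2. Make the reference in 5.5 match what 6.2 contains, either by changing the reference or by supplying in 6.2 the criterion it announces.
3. Make the second and third hemoglobin bullets of Table 5 mutually exclusive, or state which takes precedence.
4. Apply the reconciled malignancy wording when classifying the SAP Appendix A category on withdrawal criteria.

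Leave eligibility criterion 3(l) in Protocol 5.1 as it is. It restates conditions that applied during Study M16-046, and rewording it could misstate the parent study's rule.

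The cost is a few lines in an amendment or clarification letter, with no new procedures or data. Appendix E of the protocol shows that the sponsor has already revised the gastrointestinal perforation wording in both sections at once.
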